The Investigator, or a responsible party designated by the investigator, must maintain a careful record of the inventory and disposition of all agents received from Novartis.

REGULATORY AND REPORTING REQUIREMENTS

It is the responsibility of the investigator to document all adverse events which occur during the investigation. An adverse event is any untoward medical occurrence in a patient or clinical investigation subject, temporally associated with the use of the medicinal product, whether or not considered related to the medicinal product. *An AE can therefore be any unfavorable and unintended sign (including an abnormal laboratory finding), symptom, or disease (new or exacerbated) temporally associated with the use of a medicinal product.* Anticipated day-to-day fluctuations of the disease under study that do not represent a clinically significant exacerbation or worsening need not be considered an adverse event.

RECOMMENDED ELEMENTS OF A SCIENTIFIC PROTOCOL
(Noted sections should only be included as applicable to your research)

32

All adverse events occurring from the first dose of investigational product until five days after the last dose must be recorded **REGARDLESS OF WHETHER OR NOT THEY ARE CONSIDERED DRUG RELATED**. In addition, any SAEs which occur as a result of protocol specific diagnostic procedures or interventions must also be reported.

It is the responsibility of the IND holder to comply with IND safety reporting as set forth in the Code of Federal Regulations, Section 312.32.

Assessment of Causality

Every effort should be made by the investigator to explain each adverse event and assess its relationship, if any, to study drug treatment. Causality should be assessed using the following categories: no (not related), or yes (reasonable possibility).

The degree of certainty with which an adverse experience is attributed to drug treatment (or alternative causes, e.g. natural history of the underlying diseases, concomitant therapy, etc.) will be determined by how well the experience can be understood in terms of the following:

- Known pharmacology of the drug
- Reaction of similar nature being previously observed with this drug or class of drug
- The event having often been reported in literature for similar drugs as drug related (e.g. skin rashes, blood dyscrasia)
- The event being related by time to drug administration terminating with drug withdrawal (dechallenge) or reproduced on rechallenge.

The investigator may change his/her opinion of causality in light of follow-up information, amending the SAE form. The causality assessment is one of the criteria used when determining regulatory reporting requirements.

Following-up of Adverse Events

Investigators should follow-up subjects with adverse events until the event has subsided (disappeared) or until the condition has stabilized.

Definition of Serious Adverse Events:

A serious adverse event is an undesirable sign, symptom or medical condition which:

- is fatal or life-threatening
- results in persistent or significant disability/incapacity
- constitutes a congenital anomaly/birth defect
- requires inpatient hospitalization or prolongation of existing hospitalization, unless hospitalization is for:
 - routine treatment or monitoring of the studied indication, not associated with any deterioration in condition (specify what this includes)

CSMC Office of Research Compliance

Reference: [ICH E6: Good Clinical Practice: Consolidated Guidance](#)

RECOMMENDED ELEMENTS OF A SCIENTIFIC PROTOCOL (Noted sections should only be included as applicable to your research)

33

- elective or pre-planned treatment for a pre-existing condition that is unrelated to the indication under study and has not worsened since the start of study drug
- treatment on an emergency outpatient basis for an event not fulfilling any of the definitions of a SAE given above and not resulting in hospital admission
- social reasons and respite care in the absence of any deterioration in the patient's general condition
- is medically significant, i.e., defined as an event that jeopardizes the patient or may require medical or surgical intervention to prevent one of the outcomes listed above

Abnormal laboratory findings (e.g., clinical chemistry, hematology) or other abnormal assessments (e.g., x-rays, scans, vital signs, etc.) that are judged by the investigator as **clinically significant** will be recorded as AEs or SAEs if they meet the definition of an AE or SAE.

Life threatening definition:

An adverse event is life threatening if the patient was at immediate risk of death from the event as it occurred (i.e. it does not include a reaction that if it had occurred in a more serious form might have caused death). For example, drug-induced hepatitis that resolved without evidence of hepatic failure would not be considered life threatening even though drug-induced hepatitis could be fatal.

Disability/incapacitating definition:

An adverse experience is incapacitating or disabling if the experience results in a substantial and/or permanent disruption of the patient's ability to carry out normal life functions.

Hospitalization definition:

Hospitalization for elective treatment of a pre-existing condition that did not worsen from baseline is not considered an AE.

Additional SAE definitions

- All Grade 4 laboratory abnormalities
- Cardiovascular events have been seen in subjects taking other compounds that inhibit ErbB2 when used in combination with or following anthracyclines and interstitial pneumonitis has been reported in subjects taking compounds that inhibit ErbB1. As a precaution, the following will be reported as a SAE:

Cardiac dysfunction will be reported as an SAE and will be defined as any signs or symptoms of deterioration in left ventricular cardiac function that are Grade 3 (NCI CTC AE) or a $\geq 20\%$ decrease in left ventricular cardiac ejection fraction relative to baseline, which is below the institution's lower limit of normal. Refer to NCI CTC AE grading of left ventricular cardiac function.

Hepatobiliary events have been seen in subjects taking lapatinib and other tyrosine kinase inhibitors. As a precaution, the following will be reported as an SAE:

- ALT $>3 \times$ ULN and total bilirubin $>2.0 \times$ ULN ($>35\%$ direct; bilirubin fractionation required).

CSMC Office of Research Compliance

Reference: [ICH E6: Good Clinical Practice: Consolidated Guidance](#)

RECOMMENDED ELEMENTS OF A SCIENTIFIC PROTOCOL
(Noted sections should only be included as applicable to your research)

NOTE: bilirubin fractionation should be performed if testing is available. If testing is unavailable and a subject meets the criterion of total bilirubin $>2.0 \times \text{ULN}$, then the event should still be reported as an SAE.

Other hepatic events should be documented as an AE or an SAE as appropriate.

SAEs, pregnancies, and liver function abnormalities meeting pre-defined stopping criteria will be reported promptly to Novartis as described in the following table once the investigator determines that the event meets the protocol definition for that event.

Type of Event	Initial Reports		Follow-up Information on a Previous Report	
	Time Frame	Documents	Time Frame	Documents
All SAEs	24 hours	"SAE" data collection tool	24 hours	Updated "SAE" data collection tool
Pregnancy	2 Weeks	Pregnancy Notification Form	2 Weeks	Pregnancy Follow up Form
Liver chemistry abnormalities:				
ALT $>3 \times \text{ULN}$ and bilirubin ^a $>2 \times \text{ULN}$ (35% direct)	24 hours	CRF	24 hours	CRF

- a. bilirubin fractionation should be performed if testing is available. If testing is unavailable and a subject meets the criterion of total bilirubin $>2.0 \times \text{ULN}$, then the event should still be promptly reported as defined.

Reporting Serious Adverse Events

Any serious adverse events which occur during the clinical study or within 30 days of receiving the last dose of study medication, whether or not related to the study drug, must be reported by the investigator. In addition, any SAEs which occur as a result of protocol specific diagnostic procedures or interventions must also be reported.

The principal investigator has the obligation to report all serious adverse events to the FDA, IRB, and Novartis Pharmaceuticals Drug Safety and Epidemiology Department (DS&E) (***For patients taking Lapatinib / Novartis drugs***).

All events reported to the FDA by the investigator are to be filed utilizing the Form FDA 3500A (MedWatch Form).

To ensure patient safety, every SAE, regardless of suspected causality, occurring

- after the patient has provided informed consent and until at least 30 days after the patient has stopped study treatment/participation
- after protocol-specified procedures begin (e.g., placebo run-in, washout period, double-blind treatment, etc.) and 30 days after the patient has stopped study treatment

RECOMMENDED ELEMENTS OF A SCIENTIFIC PROTOCOL
(Noted sections should only be included as applicable to your research)

35

- after the start of any period in which the study protocol interferes with the standard medical treatment given to a patient (e.g., treatment withdrawal during washout period, change in treatment to a fixed dose of concomitant medication) and until 30 days after the patient has stopped study treatment

must be reported to Novartis within 24 hours of learning of its occurrence. Information about all SAEs is collected and recorded on a Serious Adverse Event Report Form; all applicable sections of the form must be completed in order to provide a clinically thorough report. The investigator must assess and record the relationship of each SAE to each specific study treatment (if there is more than one study treatment), complete the SAE Report Form in English, and **send the completed, signed form by fax to ([contact]) within 24 hours to the oncology Novartis DS&E department with the provided FAX cover sheets.**

. This includes serious, related, labeled (expected) and serious, related, unlabeled (unexpected) adverse experiences. All deaths during treatment or within 30 days following completion of active protocol therapy must be reported within 5 working days.

Any SAEs experienced after this 30 days period should only be reported to Novartis if the investigator suspects a causal relationship to the study drug. Recurrent episodes, complications, or progression of the initial SAE must be reported as follow-up to the original episode within 24 hours of the investigator receiving the follow-up information. A SAE occurring at a different time interval or otherwise considered completely unrelated to a previously reported one should be reported separately as a new event. The end date of the first event must be provided.

The original copy of the SAE Report and the fax confirmation sheet must be kept within the Trial Master File at the study site.

Follow-up information is sent to the same fax number as the original SAE Report Form was sent, using a new fax cover sheet, stating that this is a follow-up to the previously reported SAE, and giving the date of the original report. Each re-occurrence, complication, or progression of the original event should be reported as a follow-up to that event regardless of when it occurs. The follow-up information should describe whether the event has resolved or continues, if and how it was treated, whether the blind was broken or not (if applicable), and whether the patient continued or withdrew from study participation.

If the SAE is not previously documented in the Lapatinib Investigator Brochure or Package Insert (new occurrence) and is thought to be related to the Novartis study drug, a DS&E associate may urgently require further information from the investigator for Health Authority reporting. Novartis may need to issue an Investigator Notification (IN), to inform all investigators involved in any study with the same drug that this SAE has been reported. Suspected Unexpected Serious Adverse Reactions (SUSARs) will be collected and reported to the competent authorities and relevant ethics committees in accordance with Directive 2001/20/EC or as per national regulatory requirements in participating countries.

To ensure patient safety, each pregnancy occurring while the patient is on study treatment must be reported to Novartis within 24 hours of learning of its occurrence.

Lack of Efficacy

RECOMMENDED ELEMENTS OF A SCIENTIFIC PROTOCOL
(Noted sections should only be included as applicable to your research)

36

“Lack of efficacy” *per se* will not be reported as an AE. The signs and symptoms or clinical sequelae resulting from lack of efficacy will be reported if they fulfill the AE or SAE definition (including clarifications).

All serious adverse events, in addition to being reported to the FDA by the investigator, must be reported by facsimile within 24 hours to Novartis Oncology.

The SAE report should comprise a full written summary, detailing relevant aspects of the adverse events in question. Where applicable, information from relevant hospital case records and autopsy reports should be included. Follow-up information should be forwarded to Novartis within 24 hours.

SAEs brought to the attention of the investigator at any time after cessation of lapatinib and considered by the investigator to be related or possibly related to lapatinib must be reported to Novartis if and when they occur. Additionally, in order to fulfill international reporting obligations, SAEs that are related to study participation (e.g., procedures, invasive tests, change from existing therapy) or are related

to a concurrent medication will be collected and recorded from the time the subject consents to participate in the study until he/she is discharged.

Pregnancy

Patients who become pregnant during the study should discontinue the study immediately.

Patients should be instructed to notify the investigator if it is determined after completion of the study that they become pregnant either during the treatment phase of the study or within five days after the treatment period.

Whenever possible a pregnancy should be followed to term, any premature termination reported, and the status of the mother and child should be reported to GlaxoSmithKline after delivery.

Section 9.0.

Statistics

Sample size calculation for prolactinomas: Sample size was computed using proportions as standard deviation for tumor reduction on the study drug was unknown. While for the data analysis we will use quantitative analysis using the Hotelling’s T², using binary data for power calculations would be inefficient as this would require a larger sample size. We could not use the quantitative analysis for power calculations, however, as we do not know the variance.

The primary outcome is a reduction in maximal size of resistant tumors. Stabilization is defined as <20% reduction in any dimension on MRI by RECIST criteria. MRIs will be performed at baseline and at 3 and 6 months.

The null hypothesis is H₀: no reduction P<0.20 vs. the alternative hypothesis H_a: P>0.40. This will give an effect size of 0.20 to detect. Exact confidence interval and significance test is obtained from the binomial distribution. The reduction is for resistant prolactinomas (Di Sarno, 2001; Delgrange, 2009). Power is >80%, using one tailed

CSMC Office of Research Compliance

Reference: [ICH E6: Good Clinical Practice: Consolidated Guidance](#)

RECOMMENDED ELEMENTS OF A SCIENTIFIC PROTOCOL
(Noted sections should only be included as applicable to your research)

hypothesis, alpha of 0.10. This gives a target sample size of 24 subjects to achieve this power.

Sample size: use one-sided exact test. $H_0: p = p_0$; $H_A: p > p_0$.

Power	alpha	P_0 : null proportion	P_1 : true proportion	N
80%	0.05	20%	30%	116
80%	0.10	20%	30%	88
80%	0.05	20%	35%	56
80%	0.10	20%	35%	44
80%	0.05	20%	40%	35
80%	0.10	20%	40%	24

Secondary MRI studies will deal with various aspects and location by MRI of these tumors. Secondary PRL statistical studies will also be carried out under secondary outcomes.

Tumor maximal size will be obtained at baseline, 3 months, 6 months after initiation of treatment. The primary hypothesis is the change from baseline to 6 months. The analysis using maximal resistant tumor size will be carried out for the specified times given above. Initially this will be by descriptive analytic and then by inferential analysis using the test for change between baseline and 6 months and change between baseline and 3 months using rank test. We will also use Hotelling's T^2 to combine both pre-post changes.

This study is in the clinical trials paradigm essentially a Phase IIa trial and thus use of alpha type 1 error is at 10%. This is sanctioned by the biostatistics section of NCI.⁴⁰ We will also analyze the secondary endpoints of Aim 1 according to the above models. Concepts behind analysis for quantitative and binary are the same though the methods are different.

Our overall target sample size is 30 subjects which includes nonfunctioning adenomas and prolactinomas, 15 to be recruited from Cedars Sinai Medical Center and 15 from Johns Hopkins Hospital and Massachusetts General Hospital. We aim to recruit 24 subjects with prolactinomas and 6 nonfunctioning adenomas.

Due to the rarity of pituitary tumors in the general population and even more rare are aggressive pituitary tumors such as we propose to study, it is difficult to do a randomized placebo controlled trial with sufficient sample size numbers to achieve adequate power. By using the subjects as their own controls, we alleviate the issues with recruitment. This is a safety and activity trial to look for a sufficient effect of the drug on tumor growth before proceeding to a larger, randomized placebo controlled trial.

Section 10.0. Quality Control and Quality Assurance

Only samples and data collected with appropriate consent will be used for the proposed analysis. Specimens and data collected under the proof of concept clinical trial of lapatinib will be coded in such a way so that other members of the research team will be unable to ascertain the identity of specific patients. All of our data will be

RECOMMENDED ELEMENTS OF A SCIENTIFIC PROTOCOL
(Noted sections should only be included as applicable to your research)

38

maintained confidentially. Data will be kept in locked file cabinets and in password protected files on computer systems.

Section 11.0 Ethical considerations relating to the trial

Subjects will be recruited from the Pituitary Center. They will be patients followed clinically. Patients will be approached regarding participation in the study and given consent forms to review at home. They will be reassured that their clinical care will not be affected if they choose not to participate. Patients will be given opportunities to ask questions and review the consent process. Once they consent and enroll in the study, their data will be deidentified for the duration of the study. All patients entering the trial will be given the study drug. There is no placebo arm. The risks of the study are related to the side effects of the study drug and patients will be monitored for this and informed on the effects. The benefits of the study are stabilization of tumor growth. There are potential conflicts of interest between the patient's need for surgical referral and participation in the research study. However, by excluding patients who would meet definite criteria for surgery, we will minimize the conflict of interest.

Section 12.0 Data Handling and Recordkeeping

Data will be maintained in separate research charts in a locked cabinet in a locked office.

The data will be entered as well into an electronic database on a password protected computer. Only study staff and the investigators will have access to these records.

Section 13.0 Financing and Insurance

Funding for this study will be through institutional funds. Patients will only be charged for the initial MRI and visual field test, as well as hormonal tests during the study period.

Section 14.0 Publication Policy

We intend to submit our research findings to relevant peer-reviewed journals for publication. We will submit data for presentation at international meetings. We will adhere to the NIH Grants Policy Statement on Sharing of Biomedical Research Resources, including the "Principles and Guidelines for Recipients of NIH Research Grants and Contracts on Obtaining and Disseminating Biomedical Research Resources: Final Notice" (64FR 72090, December 23, 1999; and described at <http://ott.od.nih.gov/NewPages/RTguide/final.html>).

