Trial design: Open label, single cohort proof of concept trial. An additional arm of the study will be for subjects treated with the study drug in malignant pituitary tumors. Three clinical trial sites, one at CSMC and the others at Johns Hopkins Hospital and Massachusetts General Hospital.

Study population: Patients will be recruited from the Pituitary Center at Cedars-Sinai Medical Center and the other two sites.

Intervention: lapatinib 1250 mg daily for 6 months. Patients will be treated with the standardized dose used in breast cancer therapy for six months (Cameron & Stein 2008; Geyer et al. 2006). The drug will be supplied by Novartis Oncology.

- a. Primary outcome variable.

Primary outcome in nonfunctioning pituitary adenomas: 40% reduction in tumor size in any dimension. Tumor size and volume will be calculated using Open Source OsiriX® Imaging Software for MacOS. MRIs will be performed at baseline and at 3 and 6 months All MRIs will be centrally read by the dedicated pituitary radiologist at CSMC.

Primary outcome in prolactinomas: 40% reduction in tumor size in any dimension.

Primary outcome in malignant pituitary tumors: Progression free survival

- b. Secondary outcome variables.

Secondary outcomes in prolactinomas:

(a) achievement of 50% reduction of PRL levels (b) PRL normalization (c) percent reduction in PRL levels (d) percent reduction in tumor volume. Tumor volume will be calculated using Open Source OsiriX® Imaging Software for MacOS. (e) correlation of tumor size and PRL reduction (f) clinical predictors of TKI response, including age, gender, duration of disease, dose and duration of dopamine agonist therapy, baseline PRL, and baseline tumor size.

Secondary outcomes in malignant pituitary tumors: partial response, complete response, mortality, 24 hour urine free cortisol levels for Cushing carcinomas, IGF-1 levels for acromegaly carcinomas.

We will correlate ErbB receptor expression with the subjects' clinical response to the study drug. This will be performed through immunohistochemistry staining of pituitary tumor slides from surgery.

Section 5.0. Selection and Withdrawal of Subjects

Inclusion criteria: Subjects with non-functioning pituitary adenomas, who have undergone at least one prior surgical resection and have demonstrated recurrence on MRI.

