Non-hematological, Grade 3 or 4	Apply maximum supportive care recommendations (see section Error! Reference source not found.) Hold lapatinib therapy until recovery to Grade \leq 1 (up to 14 days). Refer to events management instructions Section Error! Reference source not found. Grade 3 or 4 left ventricular cardiac dysfunction - please refer to specific section Error! Reference source not found. For NCI-CTCAE v3.0 Grade 3 or 4 interstitial pneumonitis or Grade 4 rash manifested as toxic epidermal necrolysis (e.g. Stevens-Johnson Syndrome etc) lapatinib must be permanently discontinued If recurrence of adverse event after drug hold / interruptions is observed, and maximum supportive care measures applied, a dose reduction by 250mg is recommended. Lapatinib should not be used at doses below 1000mg if given as monotherapy or 750mg in combination with trastuzumab. NOTE: The 750 mg dose should only be used after all supportive measures have been exhausted. (If administered in combination with paclitaxel refer to table 13)
Non-hematological, Grade 3 or 4 and adverse events NOT resolved to Grade \leq 2 within a maximum of 2 weeks from last planned administration	Action (discontinue or resume lapatinib therapy) in individual cases to be decided by the Executive Committee. Dose reductions by 250mg (up to 2 reductions) will be considered after maximum supportive care recommendations (see Error! Reference source not found.) are introduced.

Cardiac* (asymptomatic drop in LVEF or symptomatic congestive heart failure)
	
Lapatinib therapy to be discontinued permanently in case of symptomatic NYHA class III and IV CHF. Lapatinib therapy to be hold continued or resumed according to Figure 1 for patients with NYHA class I or II CHF.

Hematological adverse events: Absolute neutrophil count (ANC) <1.0 x 10⁹/L Platelets <75 x 10⁹/L Hemoglobin <9.0 g/dL (after transfusion if needed)
	
Hold chemotherapy if lapatinib given simultaneously; if the adverse event is related to chemotherapy please refer to appropriate label (until recovery to Grade ≤1). If ANC recovers to 1.5 x 10⁹/L within 7days, then merely delaying dose is acceptable. If no recovery to ANC of 1.5 x 10⁹/L within 7 days then decrease chemotherapy dose by 20%. Dose modifications for thrombocytopenia, at the start of subsequent courses of therapy are the same as recommended for neutropenia above. Next cycle should not begin until the platelet count has recovered to 100 x 10⁹/L or more.

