	
In case of multiple short interruptions of dose due to either adverse events or drug supply or other reasons the sum of days without lapatinib treatment should not exceed 21 days in any 90 day treatment period.

*Severity corresponding to NYHA criteria

RECOMMENDED ELEMENTS OF A SCIENTIFIC PROTOCOL
(Noted sections should only be included as applicable to your research)

29

Dose Delays and Dose Reductions

Treatment may be delayed, up to 2 weeks, to allow for resolution of toxicity except in the event of NCI CTCAE Grade 3 or 4 left ventricular cardiac dysfunction or NCI CTCAE Grade 3 or 4 interstitial pneumonitis (See Criteria for Evaluating Cardiac and Respiratory Events). The Investigator must consult the Novartis Medical Monitor prior to continuing therapy for any subject requiring a delay of more than 2 weeks for unresolved toxicity, but in general, such subjects should be withdrawn from the study. If treatment is delayed for reasons other than toxicity (i.e., unplanned travel or vacation, or lack of transportation to the site) and the subject has insufficient investigational product available, the subject should resume the usual dosing schedule once drug supply has been made available. However, if the subject has been off therapy for more than 2 weeks, the Investigator must consult the Novartis Medical Monitor prior to continuing therapy.

Dose reduction for drug-related toxicity is permitted; however the Novartis Medical Monitor must be consulted prior to implementing any change in dosing. Only one dose reduction is permitted per subject and subjects should not be rechallenged to a higher dose level. If a NCI CTCAE Grade 3 or 4 drug-related event (other than left ventricular cardiac dysfunction or interstitial pneumonitis) has occurred, the investigator may discuss with the Novartis Medical Monitor whether a reduction of dose is appropriate.

PHARMACEUTICAL INFORMATION

Lapatinib (NSC #727989)

Chemical Name: N-{3-Chloro-4-[(3-fluorobenzyl)oxy]phenyl}-6-[5-{{[2-(methylsulfonyl)ethyl]amino}methyl)-2 furyl]-4-quinazolinamine,

Other Names: None

Mode of Action: Dual inhibitor of epidermal growth factor receptor (EGFR or ErbB1) and ErbB2 tyrosine kinases.

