anticonvulsants	phenytoin, carbamazepine, barbiturates (e.g., phenobarbital)	
antiretrovirals	efavirenz, nevirapine, tipranivir, etravirine	
glucocortical steroids (oral only)	cortisone (>50 mg), hydrocortisone (>40 mg), prednisone or prednisolone (>10 mg), methylprednisolone or triamcinolone (>8 mg), betamethasone or dexamethasone (>1.5 mg) ²	
other	St. John's Wort, modafinil	
CYP3A4 Inhibitors		
antibiotics	clarithromycin, erythromycin, troleandomycin, flucloxacillin	1 week
antifungals	itraconazole, ketoconazole, fluconazole (>150 mg daily), voriconazole	
antiretrovirals	delaviridine, nelfinavir, amprenavir, ritonavir, indinavir, saquinavir, lopinavir, atazanavir	
calcium channel blockers	verapamil, diltiazem	
antidepressants	nefazodone, fluvoxamine	

RECOMMENDED ELEMENTS OF A SCIENTIFIC PROTOCOL
(Noted sections should only be included as applicable to your research)

gastrointestinal agents ³	cimetidine	
fruit juices	grapefruit, star fruit, and papaw	
other	amiodarone	
Miscellaneous		
antacids	Mylanta, Maalox, Tums, Rennies	1 hour before and after dosing
herbal supplements ⁴	ginkgo biloba, kava, grape seed, valerian, ginseng, echinacea, evening primrose oil	2 weeks

1. Time period between last dose of listed drug and first dose of lapatinib, required to avoid drug-drug interaction potential for toxicity (inhibitors) or loss of efficacy (inducers) that could make the patient unevaluable. Clinically appropriate substitution of drugs not on the list is recommended.
2. A standard 3-5 day course of dexamethasone at a dose following the institutions standard of care for the prevention and/or treatment of platinum-induced nausea and vomiting is allowed. Glucocortical steroid oral dose equivalents (in parentheses) to dexamethasone 1.5 mg (or less) given daily are allowed. Intravenous dosing should be considered if clinically appropriate.
3. Emetogenic chemotherapy may require 3-4 daily doses of aprepitant. CYP3A4 inhibition by oral (not IV) aprepitant may require a concurrent dose reduction of 1-2 lapatinib tablets.
4. This list is not all-inclusive; therefore, for herbal supplements not listed, please contact a Novartis Medical Monitor or Clinical Scientist.

NOTE: If future changes are made to the list of prohibited medications, formal documentation will be created and stored with the study file. Any changes will be communicated to the investigative sites in the form of a letter.

Agent Accountability

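### Table 1 allows two 250 mg reductions for unresolved Grade 3 or 4 events, against a one-reduction rule and a 1000 mg minimum stated elsewhere; recovery grade, decision-maker and other stopping rules also disagree

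*Combined protocol and SAP*

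**What the plan says.** The planned regimen is given in Section 4.0: "Intervention: lapatinib 1250 mg daily for 6 months". Five places in the protocol then govern what happens to that dose after toxicity.

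- **Section 8.0, Table 1, row for non-haematological Grade 3 or 4 events not resolved to Grade 2 or lower within two weeks.** Whether to stop or resume is "in individual cases to be decided by the Executive Committee". On dose: "Dose reductions by 250mg (up to 2 reductions) will be considered after maximum supportive care recommendations".
- **Section 8.0, Table 1, preceding row, and the paragraph headed Other adverse events.** The drug is held for at most 14 days, pending improvement to Grade 1 or lower; the paragraph also accepts a return to the baseline grade. A 250 mg step follows if the event recurs. Both places set a monotherapy minimum of 1000 mg.
- **Section 8.0, Dose Delays and Dose Reductions.** "Only one dose reduction is permitted per subject and subjects should not be rechallenged to a higher dose level". The medical monitor must be consulted before any dose change, and before treatment continues after a toxicity delay of more than two weeks, "but in general, such subjects should be withdrawn from the study".
- **Section 8.0, item 2.** Toxicity up to Grade 2 leads to a hold and restart, Grade 3 to a hold and restart at half dose, and Grade 4 to discontinuation.
- **Section 5.0, Withdrawal of Subjects.** Lapatinib is discontinued for toxicity of Grade 2 or above.

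**The concern.** These rules apply to the subjects with the most severe and slowest-resolving toxicity, and they do not give one answer. The number of reductions, the lowest dose reached, the grade that counts as recovery, the person or body that decides and the default outcome all differ between texts that are in force together. Three sites could each follow a written instruction and treat similar subjects differently. The main stake is subject safety. A secondary one is that dose received and withdrawal would depend partly on which text was consulted, in a single-arm trial whose powered group has 24 prolactinoma subjects.

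**Working it through.** **Inputs.** Starting dose 1250 mg (Section 4.0); step 250 mg (Table 1 and Other adverse events); monotherapy minimum 1000 mg (same two places); maximum number of reductions 2 (Table 1 row) or 1 (Dose Delays and Dose Reductions); half-dose restart after Grade 3 (Section 8.0, item 2).

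**1. Dose levels.** Dose after k reductions = 1250 − 250k.
- k = 1: 1250 − 250 = 1000 mg, exactly at the stated minimum.
- k = 2: 1250 − 500 = 750 mg; 1000 − 750 = 250 mg below the minimum, and 750/1000 = 0.75 of it.
- Number of steps that fit above the minimum: (1250 − 1000)/250 = 1.

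The allowance of two therefore conflicts with both the one-reduction rule and the minimum dose. The table also gives a 750 mg limit, but for use with trastuzumab, which is not part of this trial's intervention.

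**2. Half-dose rule.** 0.5 × 1250 = 625 mg; 1000 − 625 = 375 mg below the same minimum.

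**3. Recovery grade.** A Grade 3 event that has fallen to Grade 2 by day 14 has not met the Grade 1 limit in the preceding row. It also does not enter the disputed row, which requires that Grade 2 has not been reached. The two rows do not meet.

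**4. Decision and default.** The disputed row leaves stop-or-resume open, case by case, to a committee. Dose Delays sends the investigator to the medical monitor and leans towards withdrawal. No text links the two. The oversight body that Section 8.0 does set up is a DSMB (item 5).

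**5. One subject traced through the texts.** Take a lapatinib-related, non-haematological Grade 3 event, still Grade 3 at two weeks, in a subject taking 1250 mg.

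| Text | What follows |
|---|---|
| Section 5.0 | Already discontinued, because the event is Grade 2 or above |
| Section 8.0, item 2 | Held until resolved, with no time limit given there; restart at 625 mg |
| Other adverse events and preceding Table 1 row | Hold limited to 14 days; a 250 mg step only on recurrence; not below 1000 mg |
| Table 1, disputed row | Committee decides; if resumed with reduction, 1000 or 750 mg |
| Dose Delays and Dose Reductions | Monitor consulted; in general withdrawn; otherwise at most one reduction (1000 mg if the step is 250 mg) |

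A Grade 4 event adds one more conflict: item 2 discontinues it, while the disputed row allows it to resume.

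**The case against.** The fair case on the other side is that much of this is softened elsewhere. Several stronger readings that a reader might infer are not supported.

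- **That a subject at Grade 2 on day 14 has no rule at all.** This goes too far. The provision for toxicity delays of more than two weeks reaches any such subject who needs a longer hold. The mismatch between the two table rows stands; a complete gap does not.
- **That sites are free to diverge.** The medical monitor must be consulted before any dose change at every site, which lowers the risk. Restarting at 750 mg would also mean overlooking the minimum printed in the adjacent row. Neither point removes the contradiction.
- **That the committee and the monitor cannot coexist.** They could, since consulting is not deciding and withdrawal is only the general expectation. The documents simply do not connect them. The committee's absence is established only for the supplied text, from which some pages were removed.
- **That footnote 3 to the prohibited-medication table is a further breach.** Its "may require a concurrent dose reduction of 1-2 lapatinib tablets" concerns oral aprepitant given with emetogenic chemotherapy. That is an interaction adjustment, and chemotherapy is not part of this intervention.
- **That the cardiac and liver restart rules contradict the one-reduction rule.** They permit a restart at a reduced dose, with the monitor involved. What happens to a subject already at 1000 mg could be clarified, but this is not a contradiction.
- **That about 6 of 30 subjects are affected (21% × 30 = 6.3).** The 21% in Section 8.0, item 1 covers all Grade 3 and 4 events, against 7% on placebo. The disputed row covers only lapatinib-related, non-haematological events unresolved at two weeks.
- **That the efficacy result is compromised by this row.** Any plan that permits even one reduction mixes dose levels, so that effect is not specific to this defect.

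The conflicts in count, minimum dose, recovery grade, decision route and general stopping rules remain.

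**Conclusion.** The inconsistency is real and can be read directly from the protocol. Two reductions are allowed in one place and one in another. The second step lands at 750 mg against a stated 1000 mg minimum, and the half-dose rule lands at 625 mg. Recovery is Grade 2 in one row and Grade 1 (or baseline) in the neighbouring texts, and the decision route and default outcome differ. Section 5.0 and Section 8.0, item 2 conflict with the same rules.

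The size in dose terms is exact, on the assumptions that the subject starts at 1250 mg and that steps are 250 mg. The size in subjects cannot be stated, because the documents do not give the share of severe events unresolved at two weeks. The planned sample size is untouched: the target of 24 reproduces (8 or more responders; one-sided alpha 0.089 at a 20% response rate, power 0.808 at 40%) and does not depend on these rules. This is an internal inconsistency that should be corrected. It is not evidence that any one of the stated doses or rules is the wrong one.

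**What to change.** Reconcile Section 5.0 (Withdrawal of Subjects), Section 8.0 item 2, Other adverse events, the two Grade 3 or 4 rows of Table 1, and Dose Delays and Dose Reductions into a single dose-modification rule, and have every other place refer to it. That rule should state:

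- one maximum number of reductions and the resulting dose levels in mg, consistent with whatever minimum dose the protocol states;
- one recovery grade used throughout, so that consecutive rows meet;
- one decision-maker that exists in this trial, with the role of the medical monitor made explicit;
- one outcome for each toxicity grade, including events unresolved at two weeks.

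The choice of dose, grade and rule is for the sponsor and the medical monitor. The change costs protocol wording only, with no added procedures or subjects.
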